## 10. STAGE 2 PLANNED STATISTICAL METHODS

### 10.1 Determination of Sample Size

The chosen sample size of 72 subjects (i.e. 24 subjects per dose arm) is deemed sufficient to provide adequate precision to the estimation of the response rate in each treatment arm. The trial will enroll 84 subjects to allow for a discontinuation rate of 15%.

On the basis of the available data, it is assumed that the response rate on the primary endpoint will be 5% in the 0.3 mg/kg arm, 46% in the 10 mg/kg arm and at least 46% in the 3 mg/kg arm. A sample size of 24 subjects will ensure an absolute precision of +/- 8% to the evaluation of the response rate in the 0.3 mg/kg arm (assuming the response rate is 5%) and an absolute precision of +/- 20% of the response rate in the 3 mg/kg and 10 mg/kg arms (assuming the response rate is 46%).

In addition, with 24 subjects in each arm, the probability to demonstrate that the observed response rate in the 3 mg/kg and 10 mg/kg arms is larger than 10% by comparing the lower limit of the exact 97.5% two-sided confidence interval of the observed rate to 10% is larger than 0.999 (assuming the response rate is 46%)

In addition, it is planned to perform pairwise comparisons between dose arms as part of the secondary efficacy analysis. A sample size of 24 subjects per arm will ensure a power of 82% to detect a difference of 39% between two treatment arms (assuming the best response rate is 46%) with a two-sided type one error of 0.025. Consequently if the assumption of response rates of 5% in the 0.3 mg/kg arm and 46% in the 3 and 10 mg/kg arm is true, the study will be sufficiently powered (power = 82%) to demonstrate a significant superiority of any of the higher doses over the smallest dose, using an adjusted two-sided 0.025 type-one error rate.

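### Section 10.1 gives 82% power for 5% vs 46%, but 82% is the power for 7% vs 46%; the same formula gives about 87.5% under the assumed rates.

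*Protocol*

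**What the plan says.** Protocol section 10.1 assumes response rates of "5% in the 0.3 mg/kg arm, 46% in the 10 mg/kg arm and at least 46% in the 3 mg/kg arm". The smallest assumed difference from the low dose is therefore 46 − 5 = 41 points.

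Two consecutive sentences then give a pairwise power:

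- The first says that 24 per arm give 82% power for "a difference of 39% between two treatment arms", taking 46% as the best rate, "with a two-sided type one error of 0.025". With 46% in the better arm, 39 points implies 46 − 39 = 7% in the other.
- The second, introduced as a consequence of the first and conditional on 5% and 46% being true, says "the study will be sufficiently powered (power = 82%) to demonstrate a significant superiority of any of the higher doses over the smallest dose".

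No test or formula is named for either figure. Section 10.1 is the only source: SAP section 2.5 sends the reader to the protocol synopsis for sample size, and the synopsis sends the reader back to the protocol body.

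**The concern.** With the same number per arm, the same significance level and the same upper rate, 39 and 41 points cannot have the same power under one method. The second 82% looks carried over from the first sentence and not calculated.

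The comparisons concerned are the two against 0.3 mg/kg. They are the only between-dose tests with an adjusted level and a stated aim of superiority (protocol 10.3.3 and 10.6.1.3.1; SAP 4.4.1). Their only published power figure should match the rates it is said to rest on. What is at stake is the accuracy of that statement, not the adequacy of the trial.

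**Working it through.** **Inputs** (all from protocol 10.1): n = 24 per arm; two-sided level 0.025, so z = 2.2414; better rate 46%; lower rate 7% (implied by 39 points) or 5% (assumed).

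**Formula** (pooled-variance normal approximation, no continuity correction), with p̄ the mean of the two rates:

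Power = Φ{ [ |p₂ − p₁| − z·√(2p̄(1−p̄)/n) ] / √( p₁(1−p₁)/n + p₂(1−p₂)/n ) }

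**Step 1: reproduce the plan's figure, 7% vs 46%.** p̄ = 0.265.
- Null standard error: √(2 × 0.265 × 0.735 / 24) = 0.1274, and 2.2414 × 0.1274 = 0.2856.
- Alternative standard error: √((0.0651 + 0.2484) / 24) = 0.1143.
- (0.39 − 0.2856) / 0.1143 = 0.914, so power = 0.8196. This is the stated 82%.

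**Step 2: same formula at the assumed rates, 5% vs 46%.** p̄ = 0.255.
- Null standard error: √(2 × 0.255 × 0.745 / 24) = 0.1258, and 2.2414 × 0.1258 = 0.2820.
- Alternative standard error: √((0.0475 + 0.2484) / 24) = 0.1110.
- (0.41 − 0.2820) / 0.1110 = 1.153, so power = 0.8755, about 87.5%.

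The gap from the printed figure is 87.5 − 82 = 5.5 points.

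**Step 3: could another method give 82% for both pairs?** All at 24 per arm, two-sided 0.025, unstratified:

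| Method | 7% vs 46% | 5% vs 46% |
|---|---|---|
| Pooled normal | 82.0% | 87.5% |
| Unpooled normal | 87.9% | 92.7% |
| Continuity-corrected normal | 70.9% | 78.2% |
| Arcsine | 85.7% | 91.3% |
| Fisher, exact enumeration | 77.7% | 85.3% |
| Uncorrected chi-square, exact enumeration | 85.7% | 91.4% |
| CMH-type chi-square (one stratum), exact enumeration | 85.7% | 91.4% |
| Yates chi-square, exact enumeration | 72.4% | 80.5% |

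Of these methods, only the pooled formula gives 82% for the 39-point difference. None gives 82% for both pairs: in every row power rises, by roughly 5 to 8 points, when the lower rate falls from 7% to 5%.

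**Step 4: the 3 mg/kg arm.** Its assumed rate is 46% or more. A higher rate widens the difference from 5%, so under this formula 87.5% is the minimum for that comparison.

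**The case against.** The best defence is that the paragraph states a floor. It first gives a detectable difference of 39 points at 82% power and then notes that the assumed difference is larger, so power is no less than 82%. On that reading the inference is valid, and so is the conclusion that the study is sufficiently powered. What fails is the notation: the text prints an equals sign, conditional on 5% and 46%. If a floor was meant, it has to be written as one.

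A second defence is that the size of the gap depends on a formula the protocol never names. At 5% vs 46% the methods tried run from 78.2% to 92.7%. The gap under Fisher is 3.3 points, and Yates comes within 2 points of 82%. This stands as a caution about quoting 5.5 points as though it were method-free. It does not remove the inconsistency, because Yates then gives 72.4% where the first sentence claims 82%.

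A third is that 87.5% is not the power of any planned analysis. That is correct. The protocol plans a stratified Cochran-Mantel-Haenszel test and the SAP a logistic regression adjusted for stratum. The figure is only the like-for-like counterpart of the printed 82%.

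A reader might also infer that it is unclear whether the trial was sized on a low-dose rate of 5% or 7%. The documents do not support that. Section 10.1 uses 5% throughout, as the assumption, in the precision statement and in the power sentence; 7% arises only by subtraction. Nor was the trial sized on this comparison: the synopsis and section 10.1 both justify 72 subjects by precision, and pairwise power is an addition for the secondary analysis.

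**Conclusion.** The point holds as a misattributed figure. The 82% belongs to 46% vs 7%. For the assumed 46% vs 5%, the formula that reproduces it gives about 87.5%, with exact unstratified values of 85.3% (Fisher) and 91.4% (CMH-type chi-square).

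This rests on two assumptions: that the pooled normal formula was the one used, which is inferred because it alone among the methods tried returns 82% for the 39-point difference; and that stratification is ignored, as any calculation from the inputs in 10.1 must do.

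The error understates power, so it would be wrong to conclude that the pairwise comparisons are underpowered or that 24 per arm is too few for them. The sample size, the 0.025 level and the primary comparison with 10% are all unaffected. The matter is minor.

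**What to change.** In protocol section 10.1, separate the two statements:

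- 82% is the power, with 24 per arm and a two-sided level of 0.025, for a detectable difference of 46% vs 7%.
- Under the assumed 46% vs 5%, power is about 87.5% for each comparison with 0.3 mg/kg, and at least that for 3 mg/kg, where the assumed rate is 46% or higher.

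Label both as the unstratified pooled two-proportion normal approximation, and say that they are not the power of the planned stratified test. If only a floor was intended, replacing the equals sign with at least 82% would also make the sentence true, though less informative.

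The cost is one sentence of text. No change to the design, sample size or analysis follows.

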### 10.2. Randomization and Stratification

This study is randomized with a 1:1:1 randomization ratio. A central randomization system will be used. The randomization will be stratified according to the subject's baseline hematologic status: baseline anemia (Hgb < 100 g/L and having received  $\geq 2$  units PRBC in 12 weeks prior to study entry) alone or baseline thrombocytopenia (platelet count <  $50 \times 10^9/L$ ) alone; or baseline anemia associated with baseline thrombocytopenia. The randomization system will also ensure that at least 50% of the subjects in the final study population will have baseline thrombocytopenia.

### 10.3. General considerations for statistical analysis

#### 10.3.1 Statistical Analysis Plan

The statistical section of the protocol presents the main features of the planned statistical analysis. A detailed statistical analysis plan (SAP) will be prepared by the Venn Life Sciences

statistician, validated by the sponsor and signed before the database lock prior to any unblinded statistical analysis.

Any change to the planned statistical methods will be documented in the clinical study report.

### **10.3.2 Descriptive statistics**

Quantitative variables will be described by treatment group using the following statistics: number of available data, number of missing values, mean, standard deviation, median, Q1, Q3, minimum and maximum values. When relevant, confidence intervals will also be computed.

Qualitative variables will be described by treatment group using number of available data, number of missing values, frequency counts for each category and corresponding percentage. Percentages will be calculated using the number of available data as the denominator (i.e. not including missing values). When relevant, confidence intervals will also be computed.

### **10.3.3. Inferential statistics**

The primary efficacy analysis is both descriptive and inferential. The exact confidence interval for the response rate in each arm will be computed and its lower bound will be compared to 10%.

In addition, one secondary objective of the study is to determine if there is a difference in efficacy between the three doses of PRM-151 used in the study. These comparisons will be done only if at least one dose arm is demonstrated to have a response rate superior to 10% in the primary analysis. The comparison between the 3 mg/kg arm and 10 mg/kg arm is not expected to be sufficiently powered to detect any statistically significant difference. The two main comparisons (3 mg/kg arm versus 0.3 mg/kg arm and 10 mg/kg arm versus 0.3 mg/kg) will use an adjusted type-one error rate of 0.025 to control the overall type-one error rate. The 3 mg/kg versus 10 mg/kg comparison will only be provided with an exploratory purpose and will be done without correction of the type-one error.

For all the other secondary efficacy analyses involving formal statistical comparisons, no adjustment of the type-one error rate will be conducted. As a consequence, the results of these tests will have to be interpreted bearing in mind the issue of multiplicity and the increased risk of erroneously obtaining statistically significant results.

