### **10.6.1.3. Secondary and exploratory efficacy analyses:**

#### **10.6.1.3.1. Comparison of PRR between treatment arms**

Pairwise comparisons between the three dose groups will be performed using the Cochran-Mantel-Haenszel (general association) statistic in the SAS Freq procedure, to take into account the stratified design, using the following statement:

*tables Stratum\*Treatment\*Response / cmh;*

The Breslow-Day Test for Homogeneity of the Odds Ratios will be examined to detect a potential significant stratum difference in the odds ratios.

Two pairwise comparisons (3 mg/kg versus 0.3 mg/day and 10 mg/kg versus 0.3 mg/day) will be computed with the aim to demonstrating superiority and, consequently, will use an adjusted a two-sided 0.025 level of significance.

The third comparison (10 mg/kg versus 3 mg/kg) is not expected to have enough power to demonstrate any difference with the planned sample size. This comparison is considered exploratory and will be conducted using an unadjusted 0.05 level of significance.

These analyses will be computed on both the FAS (primary analysis set) and PP analysis sets.

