4.4 EFFICACY ANALYSIS

All analyses will be performed separately for each stage.

4.4.1 Primary Efficacy Endpoint

Stage 1:

The ORR will be compared against a fixed level of 10% using one-proportion Z-test.

The hypothesis test will be performed separately in each of the 4 treatment groups and overall, each at the 5% significance level (one-sided; statistical significance will be concluded if the lower bound of the 2-sided 90% CI is above 10%).

Subjects with no post-baseline IWG response assessments will be considered non-responders.

Stage 2:

The BMRR will be described as the percent of subjects with a reduction in bone marrow fibrosis score by at least one grade from baseline to any time of the study.

The BMRR will be presented within each treatment group with the corresponding 95% CI.

The BMRR will be analyzed using a logistic regression with bone marrow response at any time during the study (yes/no) as response variable and treatment group as explanatory variable. The analysis will be adjusted on randomized stratum. Pairwise comparisons between the 3 treatment groups will be performed.

Two pairwise comparisons (3 mg/kg versus 0.3 mg/day and 10 mg/kg versus 0.3 mg/day) will be computed with the aim to demonstrate superiority and therefore, will use an adjusted two-sided level of significance of 0.025. The third comparison (10 mg/kg versus 3 mg/kg) is not expected to have enough power to demonstrate any difference with the planned sample size. This comparison is considered exploratory and will be conducted using an unadjusted two-sided 0.05 level of significance.

The protocol proposed a threshold of 10% as the lower limit for clinically relevant response. For the 3 mg/kg and 10 mg/kg groups, the lower limit of the 97.5% two-sided confidence interval will be compared to this threshold of 10%. If the lower limit of the confidence interval is above 10%, the corresponding dose will be claimed to have demonstrated clinically relevant efficacy.

For subjects with no readable post-baseline BM biopsy results available, the conservative rule to consider them as non-responders will be used.

4.4.2 Secondary Efficacy Endpoints

Stage 1:

For Stage 1, no formal hypothesis testing will be performed for the secondary efficacy endpoints. All summaries will be presented by treatment group and overall.

The bone marrow biopsy results will be analyzed as:

- Myelofibrosis grade shifts relative to baseline at Weeks 12 and 24.

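### SAP 4.4.1 runs the dose comparisons unconditionally, although protocol 10.3.3 allows them only if a dose clears 10%, so superiority could be claimed when no dose meets the sponsor's own threshold

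*Protocol*

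**What the plan says.** Protocol 10.3.3 sets an order for Stage 2. The primary analysis compares the exact lower confidence limit with 10%. On the comparisons between doses it then says: "These comparisons will be done only if at least one dose arm is demonstrated to have a response rate superior to 10" per cent in that analysis. The same section says the two main comparisons, 3 and 10 mg/kg each against 0.3 mg/kg, "will use an adjusted type-one error rate of 0.025 to control the overall type-one error rate".

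SAP 4.4.1 (Stage 2) puts the comparisons under the primary endpoint: "Two pairwise comparisons (3 mg/kg versus 0.3 mg/day and 10 mg/kg versus 0.3 mg/day) will be computed with the aim to demonstrate superiority". They "will use an adjusted two-sided level of significance of 0.025". In a later paragraph, for the 3 and 10 mg/kg groups, "the lower limit of the 97.5% two-sided confidence interval will be compared to this threshold of 10" per cent. Nothing ties one paragraph to the other, and no reason is given for leaving the condition out.

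The condition appears only in protocol 10.3.3. The protocol synopsis, protocol 10.6.1.3.1 and SAP Appendix 3 (a copy of the synopsis) describe the comparisons without it.

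The test also differs. Protocol 10.6.1.3.1 says: "Pairwise comparisons between the three dose groups will be performed using the Cochran-Mantel-Haenszel (general association) statistic". SAP 4.4.1 says: "The BMRR will be analyzed using a logistic regression with bone marrow response at any time during the study (yes/no) as response variable". It adjusts for stratum but does not say whether the p-value is Wald or likelihood ratio.

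The comparator is written per day in the synopsis, protocol 10.6.1.3.1 and SAP 4.4.1, and per kilogram elsewhere. Those passages need reconciling. The arm is called 0.3 mg/kg below.

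**The concern.** The same data can lead to different conclusions depending on which text the analyst follows. Under protocol 10.3.3, if neither upper dose clears 10%, the comparisons are not run. Under SAP 4.4.1 they are run, and a p-value below 0.025 supports a superiority statement about a dose that failed the sponsor's own relevance threshold. SAP section 1 says this SAP defines what the final study report contains, so the unconditional form is the one likely to be programmed.

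The condition also has a statistical role. When no arm truly exceeds 10%, it prevents any superiority claim unless a 10% test has first succeeded by chance. Without it, the 10% tests and the comparisons are two separate opportunities for a false claim.

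**Working it through.** **Inputs.** From protocol 10.1: 24 evaluable and 84/3 = 28 enrolled per arm; design rates 5%, 46% and at least 46%; two-sided 0.025 per comparison. From protocol 10.1 and 10.3.3: an exact 97.5% interval against 10%. All other response rates below are assumptions. Strata are ignored throughout.

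**1. The plan's own figure.** Protocol 10.1 states: "A sample size of 24 subjects per arm will ensure a power of 82% to detect a difference of 39% between two treatment arms", with a best rate of 46%, hence 46% against 7%. The pooled-variance normal approximation is

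power = Φ{[Δ − z√(2p̄(1−p̄)/n)] / √[(p₁(1−p₁)+p₂(1−p₂))/n]}.

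With Δ = 0.39, p̄ = 0.265, z = 2.2414 and n = 24, this is Φ[(0.39 − 2.2414×0.1274)/0.1143] = Φ(0.914) = 0.820. The 82% reproduces.

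**2. What clears 10%.** The lower limit L solves P(X ≥ x | n, L) = 0.0125. For n = 24, 6 responders give 8.4% and do not clear, so 7 are needed. For n = 28, 7 responders give 9.3% and do not clear, so 8 are needed.

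**3. Can a comparison succeed below that?** The single-stratum CMH-type statistic is Q = (a − t/2)²/V, with t = a + b, N = 2n and V = n²t(N−t)/[N²(N−1)]. For 6/28 against 0/28, V = 784×6×50/(3136×55) = 1.364, Q = 9/1.364 = 6.6 and p = 0.010.

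| Upper dose vs 0.3 mg/kg | 97.5% lower limit, upper dose | CMH-type p | Likelihood-ratio p | Wald p |
|---|---|---|---|---|
| 5/24 vs 0/24 | 6.0% | 0.019 | 0.006 | not usable (zero cell) |
| 6/24 vs 0/24 | 8.4% | 0.010 | 0.002 | not usable (zero cell) |
| 6/28 vs 0/28 | 7.1% | 0.010 | 0.003 | not usable (zero cell) |
| 7/28 vs 1/28 | 9.3% | 0.023 | 0.016 | 0.047 |

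If the other upper dose also misses 10%, each row is a superiority result under the SAP (CMH-type or likelihood ratio) that protocol 10.3.3 would not have tested. A Wald test never produces such a case at 24 or 28 per arm, counting a zero cell as no rejection.

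**4. Chance of a false claim.** I summed the product of three binomial probabilities over all outcomes with at least one 10% claim (3 or 10 mg/kg) or superiority claim, with every true rate set at 10%.

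With the condition, any superiority claim lies inside the event that an arm clears 10%. For n = 28, P(X ≥ 8 | 0.10) = 0.00495, so the chance is 1 − (1 − 0.00495)² = 0.0099.

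| All rates 10% | With condition | Without, CMH-type | Without, likelihood ratio | Without, Wald |
|---|---|---|---|---|
| 28 per arm | 1.0% | 2.7% | 4.1% | 1.0% |
| 24 per arm | 1.5% | 2.7% | 4.4% | 1.5% |

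False superiority alone, 28 per arm, CMH-type: 0.3% with the condition, 2.0% without.

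**5. Nominal caps.** The two main comparisons: 0.025 + 0.025 = 0.05, the same in both documents. Joint cap over the two 10% tests and the two comparisons when no arm exceeds 10%: 2 × 1.25% = 2.5% one-sided with the condition, 2.5% + 2.5% = 5% without.

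**6. Limit of the condition.** If 10 mg/kg truly responds at 46% and the other two arms at 10%, false superiority of 3 over 0.3 mg/kg (likelihood ratio, 24 per arm) is 1.83% with the condition and 1.88% without. It gives almost no protection once one dose works.

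**The case against.** Several points on the other side stand.

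- Protocol 10.3.3 assigns overall error control to the 0.025 level for the two main comparisons, not to the condition, and the SAP keeps that level. A reader might infer that the overall error now exceeds its stated bound. The documents do not support that, because the nominal 0.05 for those two comparisons is unchanged. With a CMH-type test, 24 per arm and all rates 10%, even the combined chance of a 10% claim or a two-sided rejection is 0.0423 without the condition, against 0.0187 with it. A likelihood-ratio test does give 0.069 for the two comparisons alone, but that comes from a liberal approximation at small counts.
- A reader might cite scenarios where superiority appears often with no dose clearing 10%, such as assumed rates of 2%, 10% and 10%, where a CMH-type test with 28 per arm claims superiority 16% of the time without the condition and 0.9% with it. That difference is real, so these are not false positives, and the protocol assumes 5% for the low dose, not 2%.
- A reader might infer that the SAP revoked the condition. It is only silent, as are the protocol synopsis and 10.6.1.3.1, and paragraph order in SAP 4.4.1 is not a testing order.
- SAP section 1 says a separate Stage 2 SAP (Version 2.0, 5 March 2018) was signed before the Stage 2 primary database lock. It is not supplied, so it cannot be said that the primary Stage 2 inference lacked the condition.
- SAP 2.6 calls the study non-inferential. That does not settle the matter, because SAP 4.4.1 still sets an adjusted significance level and aims to demonstrate superiority.

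**Conclusion.** The concern holds as a discrepancy between the documents that can change a conclusion. A condition stated once, in protocol 10.3.3, is missing without explanation from SAP 4.4.1 and from three other places. Following the SAP can yield a superiority claim that protocol 10.3.3 would not allow to be tested. The loss is the order from primary to secondary analysis and the joint cap when all rates are low. It is not the 0.05 cap on the two comparisons.

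The effect is modest: with 28 per arm and all rates 10%, 1.0% rises to 2.7% (CMH-type) or 4.1% (likelihood ratio), and does not change under Wald. It therefore depends on a test the SAP leaves unnamed. The figures assume exact intervals, independent binomials, no stratification and the stated rates. Whether the earlier Stage 2 SAP kept the condition is unknown.

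**What to change.** In SAP 4.4.1, state the order: first compare the 97.5% lower limits for 3 and 10 mg/kg with 10%; treat the two comparisons with 0.3 mg/kg as confirmatory only if at least one limit exceeds 10%; otherwise report them as descriptive. Name the logistic-regression test (Wald or likelihood ratio) and say how an arm with no responders is handled. Bring the protocol synopsis, protocol 10.6.1.3.1 and SAP Appendix 3 into line. If the omission was deliberate, say so and justify it; protocol 10.3.1 already requires changes of method to be documented in the study report.

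The cost is a few sentences, plus a superiority claim forgone only when no dose meets the sponsor's own threshold. At the design rates of 5%, 46% and 46% (CMH-type), the chance of at least one superiority claim is 0.977 with 24 per arm and 0.989 with 28, with or without the condition. The cost is visible only if the upper doses do much less well than planned: at assumed rates of 5%, 20% and 20% with 24 per arm, 13.0% of trials would show superiority with no arm clearing 10%, and those claims would become descriptive.
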